TITLE PAGE

New Therapeutical Perspectives in Cases of Phonological
Disorders

28053914.1.0000.5346

DOCUMENT DATE: 20/11/2018

STUDY PROTOCOL WITH SAP- STATISTICAL ANALYSIS PLAN

Objectives: The objective of this research was to analyze and compare phonological aspects such as phonetic inventory, phonological system, severity of the speech sound disorders, altered distinctive traits and phonological processes, as well as phonological and phonoarticulatory awareness, besides the auditory aspects of the abilities and variables present in Long Auditory Evoked Potential Long. Comparisons of the phonological and auditory aspects were performed before and after the intensive period of treatment in children with speech sound disorders. Twenty-five therapy sessions were assigned. The children were randomly drawn among three groups. Group 1 - Placebo: This group received no specific treatment for speech deviations, only used the computer resource to play on a website. The Group 2-Cycles Traditional: the therapy used the Modified Cycles Model. And the Group 3-SIFALA ("Speech Intervention Software"): the therapy used the proposal of the Strata Model based on Stimulability and Segment Complexity that was developed in software format. The categorization of these groups obeys the methodological questions of a randomized clinical trial. The evaluation of the children and the treatment of one of the SIFALA group were carried out by the responsible researcher. The other two groups were treated by fellowship academics of the Speech Language Pathology program. The reassessment of all procedures was performed by speech language pathologists with experience in speech and hearing areas who did not have knowledge about the variables of the research, so it was categorized as a single-blind trial. After the treatment period, the data were compared by means of the statistical analysis that used as a criterion to estimate the effects in each therapy group using the linear regression model with mixed effects for the quantitative variables responses. Also

was used the polytomous logistic model for ordinal qualitative variables. In addition, Chi-Square and Wilcoxon tests were used for analysis of the abilities and variables of Long Auditory Evoked Potential. A significance level of 0.05 was set for all tests. Most of the children treated presented gains in the phonological and auditory variables. The therapeutic models used fulfilled the objective of reorganization of the phonological system, being possible to point out as innovative and differentiated the model using *software*-SIFALA. Key Words: Children. Language. Speech Sound Disorders. Auditory Perception. Rehabilitation of Speech Sound Disorders.

STATISTICAL ANALYSIS PLAN

The variables chosen for the static analyzes characterize the phonological and auditory aspects of the evaluations applied before and after the treatment period. For the phonological aspects, we adopted the variables that determine the phonological system, dividing sounds by the following criteria: acquired, partially acquired and not acquired; (SHRIBERG et al., 1997), altered distinctive traits and phonological processes. The PCFO (SEABRA and CAPOVILLA, 2012) and the evaluation of phonoarticulator awareness – CONFIART (SANTOS, VIEIRA and VIDOR-SOUZA, 2014) were also analyzed. For the auditory aspects of the LAEP, the variables were the measures of latency and amplitude of the right and left ears, as well as the qualitative description of the occurrence of the P300 wave. The main statistical method used as a criterion for estimating the effects in each therapy group was the linear regression model with mixed effects (FAUSTO et al., 2008; PINHEIRO et al., 2017) for the quantitative response variables. This model uses fixed effect for the therapy group and random effects for children in the treatment periods, extracting information from the data more accurately than the traditional linear models, which usually use only fixed effects for the explanatory

variables. The main inferential utility of the linear regression model is related to the interpretation of the significant coefficients, with which it is possible to have an estimate for the change in the level of the phonological aspects considered in the research, among them: phonetic inventory, phonological system, distinctive features and phonological processes. The polytomic logistic model was also used for the variables of ordinal qualitative responses, which included the analysis of PCFO performance (SEABRA and CAPOVILLA, 2012) and the evaluation of phonoarticulatory awareness. (SANTOS, VIEIRA and VIDOR-SOUZA, 2014). The advantage of the application of logistic models is mainly the determination of the odds factor through the exponentiation of the estimated coefficients. Other tests involved in validating the results include Fisher's Exact, ShaphiroWilk and Levene T for correlated samples and Analysis of Variance. Chi-Square and Wilcoxon tests were applied to the PEALL variables. For all hypothesis tests, a significance level of 0.05 was set.

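### Rater and time point change together, so a before/after change within an arm cannot be attributed to therapy alone

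*Combined protocol and SAP*

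**What the plan says.** All of this is in the combined protocol and SAP.

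- **First assessment (Objectives):** "The evaluation of the children and the treatment of one of the SIFALA group were carried out by the responsible researcher".
- **Second assessment (Objectives):** "The reassessment of all procedures was performed by speech language pathologists with experience in speech and hearing areas who did not have knowledge about the" study variables. On this basis the trial is labelled: "so it was categorized as a single-blind trial".
- **Comparison of interest (Objectives):** "Comparisons of the phonological and auditory aspects were performed before and after the intensive period of treatment in children with speech sound disorders".
- **Allocation (Objectives):** "The children were randomly drawn among three groups", one of them Placebo.
- **Main method (Statistical Analysis Plan):** "The main statistical method used as a criterion for estimating the effects in each therapy group was the linear regression model with mixed effects", for quantitative responses. Its terms are described thus: "This model uses fixed effect for the therapy group and random effects for children in the treatment periods".
- **Supporting tests (Statistical Analysis Plan):** the list of tests used to validate results includes "T for correlated samples and Analysis of Variance". Chi-square and Wilcoxon tests are assigned to the evoked-potential variables, without saying whether Wilcoxon is the paired or the two-sample form.

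The Objectives section also concludes that most treated children gained on the phonological and auditory variables. It states no contrast with Placebo for that conclusion.

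**The concern.** If one person scores before treatment and others score after it, a systematic difference in how they score appears as change. More lenient second raters would produce apparent gains in an arm where nothing happened, and stricter ones would hide real gains. Many of the phonological outcomes are classifications: a sound acquired, partially acquired or not acquired, a trait altered, a process present. Such classifications can differ between scorers.

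The documents describe no common rater across the two time points, no calibration or agreement check, no rescoring of the first assessment, and no rater term in the model. At stake are the estimated effects in each therapy group, the paired t-test, the Wilcoxon test if it is the signed-rank form, and the conclusion that treated children improved.

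**Working it through.** **Step 1. Who rated when.** The text separates evaluation from reassessment. The first is given to the responsible researcher. The second covers all procedures and is given to clinicians unaware of the study variables. Two readings are needed: that the evaluation is the pre-treatment one, and that the researcher was not among the reassessors. Both follow naturally from the wording, since the researcher knew the variables. No endpoint then keeps the same rater.

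**Step 2. What each comparison estimates.** Let δⱼ be the true mean change in arm j and b a rater shift common to all arms.

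- Within arm j, expected change = δⱼ + b. That arm's data alone cannot separate the two.
- Arm j against Placebo, expected difference in change = (δⱼ + b) − (δ₀ + b) = δⱼ − δ₀. The shift cancels.

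The plan names a fixed effect for group but no group-by-time term, and no comparison of reassessment values adjusted for the pre-treatment value. The contrast that removes b is therefore available from the design but not specified.

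**Step 3. Illustrative size.** The plan has no figure to reproduce. Alpha of 0.05 is from the documents; two-sided testing is assumed. Also assumed are n = 8, 10, 15 or 20 per arm, correlation r = 0.5, 0.7 or 0.8, a rater shift d = 0.2, 0.3 or 0.5 SD of the score, and no true change.

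- SD of the change = √(2(1 − r)), in units of the score SD.
- Noncentrality = d√n / √(2(1 − r)).
- Rejection rate = probability that a noncentral t with n − 1 degrees of freedom falls outside ± the 97.5% point of the central t.

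The lowest rate always occurs at n = 8, r = 0.5 (SD of change 1.000, critical value 2.365). The highest occurs at n = 20, r = 0.8 (SD of change 0.632, critical value 2.093).

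| Shift d | Noncentrality, lowest | Rejects | Noncentrality, highest | Rejects |
|---|---|---|---|---|
| 0.2 | 0.2 × √8 / 1.000 = 0.566 | 7.8% | 0.2 × √20 / 0.632 = 1.414 | 26.9% |
| 0.3 | 0.3 × √8 / 1.000 = 0.849 | 11.4% | 0.3 × √20 / 0.632 = 2.121 | 52.1% |
| 0.5 | 0.5 × √8 / 1.000 = 1.414 | 23.2% | 0.5 × √20 / 0.632 = 3.536 | 91.8% |

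**Step 4. Check that the between-arm contrast is protected.** A separate simulation used 20,000 trials per setting with no therapy effect. The shift was expressed in SDs of the change score, so its rates are on a different scale from the table above. With 10 children per arm and shifts of 0, 0.2, 0.5 and 0.8, the within-arm test rejected in 4.7%, 8.5%, 29.7% and 61.4% of trials. The two-sample test on change rejected in 5.0% at each shift. With 5 or 20 per arm the two-sample test also stayed between 4.8% and 5.3%.

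**The case against.** The strongest reply is that this is a randomised trial with a Placebo arm and single-blind reassessment, and that its main method is a mixed model with a group effect. The paired t-test appears once, among supporting tests, with no endpoint assigned to it. This stands in part. A reader might infer that nothing in the data can separate rater from therapy; the documents do not support that, because Placebo carries the same change of rater and a common shift cancels against it. But the plan speaks of effects in each therapy group and specifies no contrast of change, so the main analysis is unclear rather than shown to be safe.

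Other stronger readings also fail:

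- **That the first assessment was unblinded to allocation.** The documents do not say whether it came before the random draw. If it did, the researcher could not have known the allocation. The point needs only a change of rater.
- **That speech was judged by ear and waves read by eye.** The scoring methods are not described. Latency and amplitude are listed as measures, and any shift may be smaller for them.
- **That Wilcoxon is a before/after test.** The form is not stated.
- **That the trial's error rate is 92%.** That figure needs the extreme value of every assumed input. The documents give no evidence that a shift occurred.

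**Conclusion.** The point holds for within-arm claims. As the documents read, rater and time point are confounded in every arm, so a before/after gain cannot be credited to therapy alone, and that includes the stated conclusion that treated children gained. It does not invalidate the randomised comparison. A shift common to the arms cancels there, although one that differs by arm or by severity would not.

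The rates of 8-27%, 11-52% and 23-92% show what shifts of 0.2, 0.3 and 0.5 SD would do to a paired t-test under the assumed sample sizes and correlations. They do not estimate what happened in this trial. The point rests on reading the evaluation as the pre-treatment one and the reassessors as different people.

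**What to change.** 1. Define the treatment effect for each endpoint as a between-arm contrast. Either compare reassessment values between arms with the pre-treatment value as a covariate, or add a group-by-time term to the existing mixed model and report that. Use the equivalent contrast in the ordinal logistic model for ordinal outcomes.
2. Report within-arm change descriptively only, state that the two assessments were scored by different raters, and do not offer paired t or signed-rank p-values as evidence of efficacy. State which Wilcoxon test was used. Reword the conclusion about gains to match.

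Both steps use data already collected. The cost is the loss of within-arm p-values and some re-analysis, since the text is in the past tense and already reports results. The group-by-time route is the smaller change to the existing model. Models for ordinal outcomes and P300 occurrence may be hard to fit if arms are small.

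If recordings and traces from the first assessment were kept, having the reassessors rescore them in random order would be a useful sensitivity check. It is optional.

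### The document labelled protocol with SAP concludes that the therapies worked beside a statement that most treated children gained, with no comparison with the randomised Placebo group

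*Combined protocol and SAP*

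**What the plan says.** The title page labels the document "STUDY PROTOCOL WITH SAP- STATISTICAL ANALYSIS PLAN" and carries "DOCUMENT DATE: 20/11/2018". No date is given for enrolment, treatment or analysis.

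The Objectives section describes random allocation to three groups: Placebo (Group 1), Modified Cycles (Group 2) and the SIFALA software (Group 3). Of Group 1 it says: "This group received no specific treatment for speech deviations, only used the computer resource to play on a website". The aim is to analyse and compare phonological and auditory aspects, and the comparison described is before versus after the treatment period. The text is retrospective: "After the treatment period, the data were compared by means of the statistical analysis".

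The closing lines of that summary, just before the Statistical Analysis Plan heading, give an outcome, "Most of the children treated presented gains in the phonological and auditory variables", then a conclusion, "The therapeutic models used fulfilled the objective of reorganization of the phonological system". One arm is then singled out, "being possible to point out as innovative and differentiated the model using" the SIFALA software. None of the three statements carries a number, a split by group or a reference to Group 1.

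The Statistical Analysis Plan section makes a linear mixed model the main method, aimed at the effect within each therapy group. The terms it names are a fixed effect for group and child-level random effects over the treatment periods. Among its other tests are a t test for correlated samples and analysis of variance. All tests are at the 0.05 level.

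**The concern.** There are two linked problems.

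The first is what the conclusion rests on. The trial randomised a group without specific speech treatment, so the effect of a therapy is the difference between its group and that one. A statement that most treated children gained is a before/after statement. Maturation, repeated testing and regression to the mean can each produce gains in children selected for a speech disorder, whether or not therapy adds anything. The same gap affects the remark favouring SIFALA, which needs a comparison with Group 2 as well as with Group 1.

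The second is the status of the document. Readers tend to treat 0.05-level tests in a dated SAP as confirmatory. A text that already contains the outcome and the conclusion was written after the data were available, so it cannot itself show that the analysis was fixed beforehand.

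At stake is whether a reader takes the closing statement as a controlled, confirmatory finding about two therapies when the document shows neither property.

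**Working it through.** The documents state no sample size, group size, SD, response rate or definition of a gain. There is therefore no design figure to reproduce. The check has two parts.

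**1. Does the text supply a controlled basis for the conclusion?**

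| Element | What the document gives |
|---|---|
| Control group | Randomised Group 1 (Objectives) |
| Comparison described | Before versus after treatment (Objectives) |
| Target of the main model | Effect within each therapy group (Statistical Analysis Plan) |
| Fixed effects named | Therapy group only |
| Time term, group-by-time interaction | Not named |
| Contrast with Group 1 | Not named |
| Primary endpoint, definition of a gain | Not given |
| Evidence beside the conclusion | Most treated children gained |

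If before and after scores are both responses and group is the only fixed effect, the group coefficient is a difference in level averaged over the two occasions. It mixes the baseline difference with the after difference and is not a difference in change. If the response is instead the change score, the group coefficient is the required contrast. The document does not say which applies. The t test for correlated samples compares a group with itself, so it is uncontrolled on its own.

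It is also unclear whether the children described as treated include Group 1. If they do, the statement pools all arms. If they do not, it omits the control. Neither reading isolates a treatment effect.

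**2. How informative is a finding that most children gained?** (Illustration; every input is assumed.)

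Let the change score be normal with a mean of d SDs, where d is drift unrelated to specific treatment, and let a gain be any change above zero. With zero treatment effect, the share gaining is Phi(d):

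- d = 0: Phi(0) = 0.50
- d = 0.25: Phi(0.25) = 0.60
- d = 0.5: Phi(0.5) = 0.69
- d = 1.0: Phi(1.0) = 0.84

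Now let each of n children gain independently with probability p, again with no treatment effect. The chance that more than half gain is P(X ≥ n/2 + 1), with X binomial(n, p) and n even:

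| n (threshold) | p = 0.5 | p = 0.6 | p = 0.7 | p = 0.8 |
|---|---|---|---|---|
| 10 (≥ 6) | 0.38 | 0.63 | 0.85 | 0.97 |
| 20 (≥ 11) | 0.41 | 0.76 | 0.95 | 1.00 |
| 30 (≥ 16) | 0.43 | 0.83 | 0.98 | 1.00 |

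With d = 0.25 (p about 0.6) and 20 children, a majority gains about three times in four. With d = 0.5 (p about 0.7) it does so about 19 times in 20. Even with no drift (p = 0.5) it happens about 4 times in 10.

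**The case against.** The case against has real force and limits the point in five ways.

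- **Success criterion.** A reader might infer that the plan made a majority of gainers its criterion for success. It states no such criterion. The outcome and the conclusion are neighbouring sentences, and nothing says that one was derived from the other. What can be said is that no other evidence stands beside the conclusion.
- **Timing.** A reader might infer that the analyses were chosen after the data were seen. The past tense and the reported outcome show when this text was written, not when the methods were chosen. A dated earlier plan may exist elsewhere.
- **No controlled analysis.** A reader might infer that Group 1 was never used. The documents do not support that: the aim is to compare, group is a fixed effect in the main model, and analysis of variance is listed. A controlled comparison may well have been run; none is reported or named as the basis of the conclusion.
- **Purpose of Group 1.** The document does not say that Group 1 was included to remove maturation or retest effects. It says only that the grouping follows the methodology of a randomised trial. The argument here needs only the fact of randomisation.
- **Magnitude.** The drifts, probabilities and sample sizes come from nowhere in the documents. A normal change score without ties also fits poorly with ordinal awareness scores, acquisition categories or P300 occurrence, and the closing sentence covers many variables at once. The percentages illustrate a general weakness and measure nothing in this trial.

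The core stands. However the gains arose, a gain among treated children cannot by itself support a therapy conclusion in a trial with a randomised control, and the text offers nothing more.

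**Conclusion.** The concern holds in a limited form. The stated conclusion is uncontrolled although the design is controlled, and this document by itself cannot demonstrate prespecification. The first part rests on the text alone: results and a conclusion appear without any between-group figure, and the analysis section names no time term, interaction or contrast with Group 1.

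The size cannot be established from the documents. The 60%, 69% and 84% figures depend on an assumed positive drift and a normal change score; they show only that the evidence offered does not separate an effective therapy from an ineffective one.

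It does not follow that the therapies had no effect, that no comparison with Group 1 was made, or that the analysis was chosen with the results in view. The documents settle none of these.

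**What to change.** 1. Base the conclusion on three contrasts in change, or in baseline-adjusted after scores: Group 2 versus Group 1, Group 3 versus Group 1, and Group 3 versus Group 2. A group-by-time term in the mixed model is one way to obtain them. Report each estimate with its 95% confidence interval.
2. Withdraw the statement that the models met their objective unless the contrasts with Group 1 support it. Apply the same test to the remark about SIFALA, using the contrast with Group 2 as well.
3. Define a gain, and say whether the children described as treated include Group 1.
4. Supply a dated plan written before the data were seen. If none exists, label the analysis retrospective and its p-values exploratory.

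The cost is rewording and a small amount of further analysis. The before and after measurements needed should already be held, so no new data are required. The downside is a possibly less favourable claim.

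### P300 occurrence is recorded twice in each child, but the plan names no paired or baseline-adjusted method for it; the only candidate test is an unspecified Chi-Square

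*Combined protocol and SAP*

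**What the plan says.** The Objectives section sets a pre/post design for the auditory outcomes: "Comparisons of the phonological and auditory aspects were performed before and after the intensive period of treatment in children with speech sound disorders". The Statistical Analysis Plan repeats this, describing its variables as characterising the phonological and "auditory aspects of the evaluations applied before and after the treatment period".

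Among the LAEP variables the SAP names latency and amplitude for each ear, "as well as the qualitative description of the occurrence of the P300 wave". P300 occurrence is the only qualitative entry in that list.

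The tests appear twice, both times as a pair and without matching test to variable. The summary closing the Objectives section says "Chi-Square and Wilcoxon tests were used for analysis of the abilities and variables of Long Auditory Evoked Potential". The end of the SAP says "Chi-Square and Wilcoxon tests were applied to the PEALL variables"; PEALL is not spelled out, and I read it as the same evoked potential.

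The other methods do not evidently cover P300 occurrence:

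- The mixed-effects model is "for the quantitative response variables".
- The polytomous logistic model is for ordinal responses, and those named are PCFO and phonoarticulatory awareness.
- Among the supporting tests, Fisher's Exact is unpaired and the t test for correlated samples is for means.

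No McNemar test, conditional or mixed logistic model, GEE, or baseline-adjusted categorical analysis is named.

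**The concern.** The plan respects pairing for its quantitative outcomes, through random effects for children and a correlated-samples t test. The one qualitative LAEP variable has no such provision. Taken literally, a Chi-Square can be applied in two ordinary ways, and each has a cost.

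- **Occurrence by time, within an arm.** Each child enters the table twice, as if two different children had been measured. The information about change lies in children who gain or lose the wave, and that table does not show them. The test's error rate is not the stated 0.05.
- **Post-treatment occurrence by arm.** The test is sound, but each child's baseline status, already collected, is left out and the comparison is less precise than it could be.

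At stake is how far any statement about P300 gain can be relied on. The document's summary reports auditory gains in most treated children, which is a statement about change within a child.

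**Working it through.** The documents give no P300 figure, sample size or power to reproduce. Everything numerical below uses assumed inputs. The level of 0.05 is from the SAP; two-sided testing is assumed, since sidedness is not stated.

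**1. Level of an unpaired Chi-Square of occurrence by time.** Let n children have the same occurrence rate p before and after, with within-child correlation phi.

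- Variance the Chi-Square assumes for the difference in proportions: 2p(1−p)/n.
- True variance: 2p(1−p)(1−phi)/n.
- Actual large-sample level: P(|Z| > 1.96/√(1−phi)).

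| Assumed phi | 1.96/√(1−phi) | Actual level |
|---|---|---|
| 0 | 1.96 | 5.0% |
| 0.3 | 2.34 | 1.9% |
| 0.5 | 2.77 | 0.6% |
| 0.7 | 3.58 | 0.03% |

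Simulation (40,000 runs per setting, 20 children, p = 0.5) gave 1.7% at phi 0.3 and 0.6% at phi 0.5, in line with the formula.

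**2. One table, several realities.** Suppose 8 of 20 children have the wave before and 15 of 20 after. Chi-Square = 40 × (8×5 − 15×12)² / (20×20×23×17) = 5.01, p = 0.025, regardless of who changed. McNemar's test does depend on who changed:

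| Gained, lost | Chi-Square p | Exact McNemar p | Asymptotic McNemar p |
|---|---|---|---|
| 7, 0 | 0.025 | 0.016 | 0.008 |
| 8, 1 | 0.025 | 0.039 | 0.020 |
| 9, 2 | 0.025 | 0.065 | 0.035 |
| 10, 3 | 0.025 | 0.092 | 0.052 |

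**3. Power within an arm.** Assumed: 20 children, occurrence rising from 40% to 70%, simulated as above.

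| Assumed phi | Unpaired Chi-Square | Asymptotic McNemar | Exact McNemar |
|---|---|---|---|
| 0 | 0.47 | 0.44 | 0.34 |
| 0.3 | 0.45 | 0.59 | 0.45 |
| 0.5 | 0.45 | 0.83 | 0.56 |

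Under no change, with 20 children and p = 0.5, asymptotic McNemar had a level of 4.3%, 4.5% and 5.0% at phi 0, 0.3 and 0.5; exact McNemar had 2.3%, 1.5% and 0.9%. The exact version gives up much of what pairing gains.

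**4. Post-treatment comparison of two arms.** Assumed 40% against 70%, 80% power, two-sided 0.05: 42 children per arm without baseline. Taking the variance reduction from baseline adjustment as roughly 1 − phi²:

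- phi 0.3: 42 × 0.91 = 38.2, so 39 per arm.
- phi 0.5: 42 × 0.75 = 31.5, so 32 per arm.
- phi 0.7: 42 × 0.51 = 21.4, so 22 per arm.

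This is an approximation on the linear scale. It shows the order of the loss and is not a sample-size calculation for this trial.

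**The case against.** The strongest reply is that the plan does not specify a wrong test; it leaves the test unspecified. Four parts of that reply deserve an answer.

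- **The link from Chi-Square to P300 occurrence is inferred.** This stands. The two tests are assigned jointly, the Objectives wording also mentions abilities, and no categories for occurrence are given. The inference is still the natural one: Wilcoxon fits latency and amplitude, and P300 occurrence is the only qualitative LAEP variable listed.
- **Other readings exist.** Chi-Square could loosely mean McNemar's chi-square, or a comparison of arms on change categories. Either would remove the pairing problem. This stands as a possibility, but neither is written down, so a reader cannot rely on it.
- **The post-treatment comparison is not biased.** This stands in full. A reader might infer that children who always had a wave count as therapy successes and tilt the result. Under randomisation such children are expected equally in every arm, and chance imbalance is already part of the test's sampling error. Only precision is lost.
- **Pairing does not guarantee more power.** A reader might infer that Chi-Square would miss real gains that exact McNemar would find. That does not hold generally. With 10 of 20 before and 16 of 20 after, Chi-Square = 40 × (10×4 − 16×10)² / (20×20×26×14) = 3.96, p = 0.047 uncorrected. If 6 gained and none lost (phi = 0.5, the highest these margins allow), exact McNemar gives 2 × 0.5⁶ = 0.031. If 7 gained and 1 lost (phi = 0.25), it gives 2 × (1+8)/256 = 0.070, so the exact paired test is then the one that falls short.

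What remains is that no paired or baseline-adjusted categorical method is named for a variable measured twice in each child.

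**Conclusion.** The point holds as a minor one. Followed literally, with Chi-Square in its ordinary sense, the plan either ignores the pairing of P300 occurrence or leaves out its baseline value.

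- On the before/after reading, the error rate is wrong in the conservative direction when within-child correlation is positive: about 1.9% and 0.6% for assumed phi of 0.3 and 0.5. The p-value is also blind to individual gains and losses. False positives from this source are not expected under positive correlation.
- On the post-treatment reading, the test is valid and the loss is precision: for assumed rates of 40% and 70% and phi 0.5, about 42 against 32 children per arm.

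The documents do not support saying that an incorrect test was definitely used or that true P300 gains were missed. The number of children, the P300 rates, the within-child correlation and the compared quantities are all unstated, so the size in this trial cannot be fixed. P300 occurrence is also not identified as a primary outcome.

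**What to change.** In the SAP, state which comparison P300 occurrence serves and name the test for it.

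1. Main analysis: compare arms on post-treatment occurrence, adjusted for baseline occurrence, by penalised or exact logistic regression or by an exact test stratified by baseline occurrence.
2. Description: for each arm, tabulate children as wave gained, kept, lost or never present.
3. Change within an arm: replace any unpaired Chi-Square by McNemar's test, preferably mid-p or asymptotic. In the example of 7 gained and 1 lost, mid-p is 18/256 − 8/256 = 0.039, against 0.070 for the exact version.

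If Chi-Square already meant McNemar's test or a comparison of change categories, say so; the wording is then the only change for that analysis.

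The cost is a paragraph of SAP text and a re-run on data already collected. The downside is that exact McNemar, if chosen, can have less power than the unpaired Chi-Square when within-child correlation is low (0.34 against 0.47 at phi 0, for the assumed 20 children and 40% to 70%). That is why the less conservative versions are preferred, and why the between-arm comparison should carry the inference about therapy.
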